### 9.3 Sample Size and Accrual

We propose to have 60 subjects to give clinical and histological endpoints of interest at the primary assessment time of 4 weeks post graft. We expect no more than 6 subjects to potentially drop out of the study before providing Week 4 data, and thus will enroll 66 patients in total. With an estimated enrollment of 1 out of 5 screened patients, we expect to have a pool of over 330 patients over two years from which to select 66 subjects (33 subjects per group over two years) that will be randomized equally to one of the two groups - EVPOME and POM grafts. The randomization list will be prepared electronically in advance by the biostatistician and transferred to the MICHR statistics group for incorporation into the TATUM system. Randomization will be stratified by smoking status.

The primary clinical endpoint is the degrees of keratinized tissue. Secondary outcomes are contracture and wound healing index. Ancillary endpoints include the presence or absence of a continuous epithelial layer, the degree of vascular ingrowth, the LDF measurement of gingival blood flow. The main aim is to show that EVPOME treatment give comparable clinical and histological results when compared with POM treatment. It is also expected that the EVPOME will cause less patient discomfort and pain, and have a better color rendition to the surrounding tissue than the POM. Hence, we expect EVPOME to show better outcomes for pain, color rendition, and microvessel infiltration than POM, while showing comparable outcomes on primary endpoints of keratinized tissue and graft contracture or histological endpoints compared with POM. Sample size is calculated to show near equivalence of the two groups for primary and secondary outcomes. Sample size calculation and power consideration are provided following the data analytic plan described for each outcome.

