### Sample Size and Population

Sixty (60) subjects, thirty (30) subjects per treatment group, will be randomized to receive either the experimental treatment, EVPOME (Group 1), or standard of care, the palatal oral mucosa (POM) graft (Group 2). The study population will include non-smoking adults (ages 18 and older) in need of additional keratinized oral mucosa.

Subjects will be recruited from UMHS through clinic referrals and the UMHS clinical research web portal for UMClinicalStudies as well as the University of Michigan (U-M) School of Dentistry, and their graduate periodontics clinic. Subjects may be also be recruited via Clinicaltrials.gov.

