### 3. STUDY DESIGN

This safety and efficacy study will be a single site, randomized, parallel-group autogenous ex vivo produced oral mucosa equivalent (EVPOME) vs. the “gold standard” palatal oral mucosa (POM), in subjects requiring additional keratinized oral mucosa.

A total of sixty subjects will be randomized in a 1:1 ratio to autogeneous EVPOME vs. POM. If randomized to EVPOME, the subjects will be scheduled for a harvest biopsy (Visit 2 procedure). If randomized to the POM group, the subjects will be scheduled for the graft (Visit 3 procedure). See Table 1(Section 6.1) for the Schedule of Evaluations. Subjects will be non-smoking adults (18 years and older) needing increased keratinized oral mucosa.

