#### 4.2 Exclusion Criteria

- 4.1.1. Subjects with a known sensitivity to agents used in AlloPatch® production including: Gentamicin, Cefoxitin, Lincomycin, Polymyxin B, and Vancomycin
- 4.1.2. Subjects with potential medical complications such as evidence of clinically significant (as defined by investigators) renal, hepatic, cardiac, endocrine, hematologic, autoimmune, or any systemic disease which may complicate execution of the protocol and/or interpretation of results, i.e. interfere with wound healing or be a poor candidate for general anesthesia, uncontrolled diabetic, renal failure etc.
- 4.1.3. Documented history of syphilis, HIV, Hepatitis B or C virus
- 4.1.4. Pregnant women or women planning to become pregnant or unwilling to abstain or use double barrier contraceptives during the course of the study
- 4.1.5. Known or suspected allergy to bovine (cow) protein or iodine
- 4.1.6. Current radiation therapy or history of radiation therapy treatment to the intraoral donor biopsy site or recipient site for graft placement.
- 4.1.7. Smoking or use of tobacco products within 6 months prior to screening (subjects who quit smoking > 6 months prior to screening will be considered former smokers)
- 4.1.8. History of either alcohol or drug abuse in the past 5 years
- 4.1.9. Participation in another clinical trial within 30 days of screening
- 4.1.10. Subjects taking medications that can result in gingival enlargement/overgrowth (Cyclosporine, Dilantin, calcium channel blockers)
- 4.1.11. Current use of a medication used to treat a thyroid disease.
- 4.1.12. Current use of intravenous anti-resorptive therapies or a history of intravenous antiresorptive therapies during the past 5 years
- 4.1.13. Prior successful or attempted graft placement at the study defect site
- 4.1.14. Any physical or mental condition which in the opinion of the Investigator or Medical Monitor may interfere with the subject's ability to comply with the study procedures

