### 4.3 Study Enrollment Procedures

The clinical treatment site will maintain a screening and enrollment log to track screen failures and enrollment (See Appendix A). A subject will not be screened until an Informed Consent Form has been signed. A subject's reason for ineligibility and reasons for nonparticipation or withdrawal from the study will be documented for inclusion in the Trial Master File (TMF).

Subjects who appear to meet the criteria for study participation will be informed of the study and, if interested, will review the study consent(s) with a qualified individual (approved by the PI to administer consent and listed on the Delegation of Authority Log).

During the informed consent process, study staff will detail the study procedures to ensure that the subject understands the study procedures and what is involved prior to signing the informed consent document. Subjects will be informed that they can withdraw from the study at any time and receive alternative care outside of the study. Subjects will be afforded as much time as needed to make an informed decision regarding willingness to participate in the study. Additionally, the study staff will provide contact information and will be available to discuss any questions or concerns potential subjects may have.

At the time of enrollment, immediately after written informed consent is obtained and before performing any study-related procedures, each subject will be assigned a unique sequential subject number for identification throughout the study by the study staff. This subject number will not be reused for any other participant in the study.

Once a subject has successfully met all inclusion and exclusion criteria, the subject will be randomized using the random number generator in a 1:1 ratio to EVPOME or POM via the web-based Treatment Assignment Tool U-M (TATUM) to obtain the subject's treatment assignment. The randomization schedule will begin with block sizes of 2, 4, or 6.

Upon randomization, an email will be sent to the Co-Investigator and/or any appropriate study staff. Randomization numbers will be assigned in the order in which subjects qualify for treatment, not in the order of study enrollment.

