## 9. STATISTICAL CONSIDERATIONS

### 9.1 General Design Issues

This is a randomized, parallel-group (autogenous *ex vivo* produced oral mucosa equivalent (EVPOME) vs. palatal oral mucosa (POM)) safety and efficacy study in subjects requiring additional keratinized oral mucosa for dental rehabilitation. The primary hypothesis is that EVPOME is an equivalent intraoral grafting material when compared to POM in regards to keratinized tissue and graft contracture, but is superior to POM in regards to pain, color rendition, and microvessel infiltration.

The comparison will be done using primary efficacy measures of enhanced keratinization, and secondary measures of graft contracture and wound healing index, and ancillary measures of increased microvessel ingrowth. Clinical assessments will include postoperative pain. Intraoral photographs will be done at screening and at biopsy, 2, 4, 8, and 24 weeks after intra-oral grafting. Tissue biopsy will be conducted at week 4 and laser Doppler flowmetry at weeks 2, 4, 8, and 24. Primary assessment time will be at week 4, and final assessments for all subjects will be at week 24.

Subjects will be screened until we have the necessary 60 enrolled. It is likely there will be 4 screened subjects to 1 enrolled subject. All subjects will undergo informed consent prior to any screening procedures. It is expected that it will take 2.5 years to successfully enroll 60 patients. Subjects will be recruited through the Patient Admitting and Emergency Services (PAES) clinic in the U-M School of Dentistry in conjunction with MCOHR. All new patients are routed through PAES and assigned to specialty or

undergraduate clinics. Most patients do not return to the PAES clinic, so we are not likely to have redundancy. PAES had 13,100 visits in 2003. It is estimated that 40% of the western population is missing 1 or more teeth (50% to be restored with implants for our purposes). Approximately 1/3 of them are in need of soft tissue oral mucosa grafts which is a very common procedure. This will give us a population from which to draw approximately 865 new patients per year. Of this group we need to recruit 60 subjects over two years from a potential pool of 1,730 patients. With an estimated enrollment of 1 out of 4 screened patients, we should have a pool of over 400 patients per year from which to select 30 subjects. Subjects will be recruited by full-time faculty members in the Department of Periodontics at the U-M School of Dentistry.

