## 9.2 Outcomes

### 9.2.1 Primary outcome

The primary outcome will be clinical increase in zone (width) of keratinized mucosa (KM). For edentulous sites, KM width will be measured by determining the distance from the crest of the edentulous ridge to the mucogingival line to the nearest millimeter with a Castroviejo caliper. For patients with an existing implant or tooth, KM width will be measured from the implant mucosal or tooth margin to the mucogingival line.

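### Site type sets the landmark for the primary keratinized mucosa (KM) width but is neither a stratification factor nor a named covariate; the one stratifier, smoking status, has undefined levels and can only mean never versus former smoker.

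*Combined protocol and SAP*

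**What the plan says.** - Randomization, 9.3: "Randomization will be stratified by smoking status". No levels are given and no second factor is named. Section 4.3 describes allocation "in a 1:1 ratio to EVPOME or POM" with block sizes of 2, 4 or 6, and mentions no stratification.
- Population: section 3 states "Subjects will be non-smoking adults (18 years and older) needing increased keratinized oral mucosa", and the synopsis agrees. Section 4.2 excludes "Smoking or use of tobacco products within 6 months prior to screening" and adds that "subjects who quit smoking > 6 months prior to screening will be considered former smokers". Former smokers are therefore eligible and have their own label.
- Primary outcome, 9.2.1: for an edentulous site the measurement starts at the ridge crest and is made with a caliper to the nearest millimeter. Otherwise, "For patients with an existing implant or tooth, KM width will be measured from the implant mucosal or tooth margin". Section 6.3.5 lists the same three starting points.
- Analysis, 9.5 Aim 1: an equivalence test of means at Week 4 against ±0.55 mm, planned on a mean of 3.70 mm and an SD of 0.65 mm. No covariate is named. A sentence at the end of 9.5 allows adjustment, when appropriate, for graft area and geometry and for other variables including age, general health and alcohol use. Neither site type nor smoking status is on that list.

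**The concern.** A stratification factor earns its place by balancing something expected to affect the outcome, and it should then appear in the analysis. Here the factor is undefined. A current versus non-current split would put every subject in one stratum, so the factor does something only if it means never versus former, which the plan does not say.

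The baseline feature most closely tied to the primary measurement is left to chance. KM width is the distance from a starting landmark to the mucogingival line, and the landmark depends on whether the recipient site is a ridge, an implant or a tooth. If typical widths differ between these, site type adds variance to the Week 4 comparison, and an uneven split moves the estimated difference in that particular trial. The plan's equivalence power is only just above 80%, so there is little slack to absorb either effect.

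**Working it through.** **1. The plan's own figure.** Inputs from 9.5 Aim 1: SD 0.65 mm, 30 per arm, 95% CI, margin ±0.55 mm.

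- SE = 0.65 × √(2/30) = 0.168 mm (plan: 0.17).
- Margin of error = 1.96 × 0.168 = 0.329 mm (plan: about 0.33).
- Probability that the whole 95% CI lies inside ±0.55 mm when the true difference is 0: 2Φ(0.55/0.168 − 1.96) − 1 = 81.2% (plan: at least 80%).

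The figures reproduce. They use one SD for all sites and make no separate allowance for site type.

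**2. What the documents give on site type.** They give no expected mix and no KM data by type. The recruitment estimate in 9.1 starts from tooth loss ("It is estimated that 40% of the western population is missing 1 or more teeth (50% to be restored with implants"), while the title and 9.2.1 also admit sites around teeth, so the mix cannot be inferred from it. Both the share of a type and the difference between types (D) are therefore assumptions below.

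**3. Chance of imbalance.** Take 60 subjects with Week 4 data, split 30/30, with K of them having one site type. The number in one arm is hypergeometric(60, K, 30). A gap of 20 points is 6 subjects out of 30.

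| Share of the type (assumed) | K | P(gap ≥ 20 points) |
|---|---|---|
| one third | 20 | 0.170 |
| one half | 30 | 0.196 |

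Treating the arms as independent binomial samples instead gives 13% and 15%.

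**4. Size of the shift, given a 20-point gap.** Shift = 0.20 × D.

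- D = 0.5 mm: 0.10 mm, which is 0.10/0.55 = 18% of the margin.
- D = 1.0 mm: 0.20 mm, which is 36% of the margin.

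With the SE held at 0.168 mm, the probability of concluding equivalence is Φ((0.55 − shift)/SE − 1.96) − Φ((−0.55 − shift)/SE + 1.96). It falls from 81% to 74% for a 0.10 mm shift and to 54% for a 0.20 mm shift.

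**5. How plausible is D?** For two types, the between-type variance is p(1−p)D². The planned variance is 0.65² = 0.4225 mm².

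| D (assumed) | p(1−p)D², p = 1/3 to 1/2 | Share of 0.4225 |
|---|---|---|
| 0.5 mm | 0.056 to 0.0625 | 13-15% |
| 1.0 mm | 0.222 to 0.250 | 53-59% |

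If 0.65 mm already includes differences between site types, D = 1.0 mm would mean that site type explains more than half of all variation in KM width. If 0.65 mm is instead a within-type SD, the unadjusted SD becomes √(0.4225 + p(1−p)D²), and average power falls to 73-74% for D = 0.5 mm or 48-51% for D = 1.0 mm. The documents do not say which kind of SD it is.

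**The case against.** **The stratifier is not empty.** A reader might infer that stratifying by smoking in a non-smoking population is meaningless. The documents do not support that: 4.2 keeps former smokers eligible and labels them, so never versus former is a workable two-level factor. Nor do they show that this split has no prognostic value. What stands is that the levels are undefined and that the factor is missing from 4.3 and from the analysis.

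**Randomization is valid without site type.** A reader might infer that the comparison is biased. It is not. The estimate is unbiased over repeated randomizations, and if the SD includes variation between site types, the confidence interval already reflects chance imbalance. What remains is lost precision and a shift in those trials where the split happens to be uneven.

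**Part of the effect may cancel.** The primary outcome is defined as an increase in width, and each subject keeps the same landmark throughout, so a landmark offset largely drops out of a change score. The 3 mm ceiling on KM width at entry and the standard graft shape also limit the room for differences. This stands in part. However, Aim 1 is planned on a measurement averaging 3.70 mm with no baseline adjustment written, and a change score would not remove differences between site types in response to the graft.

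**Adjustment may already be allowed.** The sentence at the end of 9.5 is open-ended. But it follows the repeated-measures text, applies only when appropriate, and does not name site type. That does not pre-specify the primary comparison.

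**Conclusion.** The point holds as a gap in specification that affects precision. Smoking status is the only stratifier, its levels are not stated, and the only split that eligibility allows is never versus former smoker. Site type determines the starting point of the primary measurement and is controlled neither in the randomization nor in the Week 4 analysis.

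The size cannot be derived from the documents. Under the assumed shares, a gap of 20 points or more has a 17-20% chance; under the assumed 0.5-1.0 mm difference, a 20-point gap shifts the estimate by 0.10-0.20 mm. The lower figure is below the planned standard error of 0.17 mm. The upper one requires either that site type dominates the variation in KM width or that 0.65 mm is a within-type SD. Both would be smaller for change from baseline. The power losses in the working are conditional on the same assumptions and are not a finding that the trial is underpowered.

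Action is still warranted because the remedy is cheap and planned power is only 81%.

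**What to change.** 1. In 9.5 Aim 1, pre-specify the Week 4 equivalence comparison of KM width as a linear model with treatment, site type recorded at Visit 1 (edentulous ridge, implant, tooth) and the stratification factor actually used. Compare the 95% CI for the adjusted treatment difference with ±0.55 mm.
2. In 9.3 and 4.3, state the smoking strata as never versus former smoker, so that the randomization text and the list agree.
3. Optional, and only if the randomization list has not yet been used: stratify by site type instead of smoking status. Crossing the two would give 3 × 2 = 6 strata of about 66/6 = 11 subjects, so replacing is more workable than adding. The price is that former versus never smoking is no longer balanced by design. Step 1 does not depend on this choice.

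Cost: a few sentences and up to three extra model degrees of freedom (two for site type, one for a two-level smoking factor). Site type can be established at screening for every subject, so no new procedure is needed.

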### 9.4 Data Monitoring

No interim data analysis is planned, but accrual rates and dropout rates will be monitored every 6 months. On-site data monitoring will occur at least annually.

## 9.5 Data Analyses

The main aim of the study is to determine by quantitative outcome measures that EVPOME will function as well as POM in terms of increased epithelialized tissue, decreased contracture, and increased microvessel infiltration. It is also expected that the EVPOME will have a closer adaptation in color rendition to the surrounding tissue. Our primary comparisons will be based on the observations at four weeks post-graft.

**AIM 1 - Keratinized Tissue:** Primary comparison will be based on week 4 assessment using an equivalence test of means. Background data on measurements of keratinized tissue for POM (standard of care) gave a mean measurement of 3.70 mm with an SD of 0.65 mm. The mean and SD were relatively constant over the follow up period from 3 to 12 months. If, in this study, both EVPOME and POM give comparable results, the distribution of the mean difference in keratinized tissue with 30 subjects in each arm will be approximately normal with a mean of 0 and standard error of 0.17, and a 95% confidence interval for the true mean difference between the two procedures will have a margin of error of about 0.33 mm. This confidence interval will exclude a value for the mean difference of 0.55mm or larger with probability at least 80%. Therefore sample size will be adequate to show near equivalence of the two treatments if the degree of keratinized tissue measurement of EVPOME is within  $\pm 0.55$ mm of POM. Statistical power will be even larger if non-inferiority of EVPOME to POM is desired, where true increase in keratinized zone in EVPOME group is no less than 0.55 mm compared with the increase of zone of keratinized tissue in POM.

**AIM 2 - Shrinkage in Graft:** The percent shrinkage (contracture) in graft will be expressed as  $100*(1 - (\text{Area final}/\text{Area Day0}))$ , and the comparison will be based on week 4 assessment using an equivalence test of means (with log transformation if the data are highly skewed upon visualization). Prior data for POM gave a mean shrinkage of 25% at 4 weeks post-op with a standard deviation (SD) of about 13%. If shrinkage is about the same for both EVPOME and POM, with a sample size of 30 subjects in each group, this translates into an estimate of the mean difference with standard error of about 3.4%. This gives a margin of error of 6.6% for a 95% confidence interval, and the 95% confidence interval excluding a value for the mean difference in shrinkage as large as 11% with probability of 80%.

**Wound Healing Index (WHI):** WHI will be analyzed via the following chart, and the index will be tabulated by treatment group at follow-up visits 5, 6, 7, and 8. Depending on the observed distribution of the index, the data will either be dichotomized or considered as an ordinal data.

Scores	Criteria
1	Uneventful healing with no gingival edema, erythema, suppuration, patient discomfort, or flap dehiscence
2	Uneventful healing with slight gingival edema, erythema, patient discomfort, or flap dehiscence but no suppuration

3	Poor wound healing with significant gingival edema, erythema, patient discomfort, flap dehiscence, or any suppuration
---	---

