#### **6.2.11 Off-Study Requirements**

Subjects who discontinue early from the study for any reason after Visit 3 will be asked to return to perform study procedures as described in Visit 8/End of Study. All subjects who discontinue or complete the study will also be asked to report any Serious Adverse Events that occur within 30 days of completion/withdrawal from the study.

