### 6.3.5 Clinical Assessments

Clinical assessments include width of keratinized mucosa (KM) as determined by the distance between the crest of the edentulous ridge, the gingival margin of the tooth, or the implant mucosal margin and the mucogingival line to the nearest millimeter, graft contracture, graft color as determined by assessing tissue perfusion, postoperative pain, Wound Healing Index (WHI), color of graft tissue compared to surrounding

3/28/2017

non-grafted tissue, and oral care follow-up. These assessments will be performed at post-operative visits 5, 6, 7 and 8. Periodontal measures include Periodontal Pocket Depth (PPD – measured from gingival margin to base of periodontal pocket to nearest millimeter), gingival recession measured from cemento-enamel junction on tooth to gingival margin, Clinical Attachment Level (CAL- determined by subtracting the gingival recession from PPD), and bleeding on probing (BOP) determined as present (1) or absent (0),

Visual analog scale for pain will be assessed for groups, I (at time of harvest of biopsy and EVPOME placement) and group II at time of harvesting of palatal donor graft and grafting at recipient site.

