**Laser Doppler Flow (LDF):** LDF data will be compared based on gingival blood flow at Week 4 post-surgery at the graft site between the EVPOME and POM groups. One aspect of this study will be to examine and explore the usefulness of this measure. In particular, we will explore the use of control measures taken on normal tissue to help adjust for intra subject factors contributing to the variability. The primary investigation will compare gingival blood flow at the graft site at two weeks, four weeks, eight weeks, and 24 weeks post-surgery to the values in an analysis of covariance (ANCOVA) model. The corresponding differences at the control site will also be incorporated as a covariate to partially adjust for intra-individual variability. More detailed analyses will utilize ANCOVA methods for repeated measures. There is relatively little background data on the use of LDF to measure perfusion in the context being studied here though some preliminary data on measuring gingival blood flow can be found in Justus et al. where change in gingival blood flow from baseline to post surgery (over the period 7 to 24 .days) was found to have a mean of about -25 perfusion units (PU) with an SD of about 60 PU. The measurement is highly variable.

For repeatedly measured data such as pain and wound healing index, data will be

summarized by treatment groups at each follow-up time. In addition, linear mixed-effects models will be used to make the between group comparison while adjusting for potential within person correlation of the outcome variables. By using the modeling approach, it will be possible to incorporate all observations from both treatment groups and make between treatment group comparisons efficiently using a treatment dummy indicator. The model will allow us to not only compare the time-averaged means, but also allows us to explore the rate of decline between the EVPOME and POM groups such as the rate of decline in pain, using appropriate interactions terms. When appropriate, comparisons between treatments will be adjusted for surface area of the graft as well as measures of its geometry, and other variables including age, general health and alcohol use.

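### AIM 1 tests Week 4 means with no analysis set or missing-data rule and leaves the Week 2 reading unused, so loss of poor EVPOME healers before Week 4 could inflate false equivalence

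*Combined protocol and SAP*

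**What the plan says.** - **Primary test.** Section 9.5, AIM 1: "Primary comparison will be based on week 4 assessment using an equivalence test of means". Equivalence is judged by a 95% confidence interval against 0.55 mm in either direction. Neither AIM 1 nor the rest of Section 9 names an analysis population or says what happens when the Week 4 value is missing.
- **Expected loss.** Section 9.3: "We expect no more than 6 subjects to potentially drop out of the study before providing Week 4 data". The response is to enrol 66 so that 60 supply Week 4 data. No split by arm, timing or reason is given.
- **Other KM readings.** Section 6.3.5 includes KM width among the clinical assessments and adds: "These assessments will be performed at post-operative visits 5, 6, 7 and 8". These are Weeks 2, 4, 8 and 24.
- **Repeated-measures model.** In Section 9.5, after the Laser Doppler text: "linear mixed-effects models will be used to make the between group comparison". Pain and the Wound Healing Index are given as examples. KM is not named, and AIM 1 does not refer to this model.
- **Exit visit.** Section 6.2.11: "Subjects who discontinue early from the study for any reason after Visit 3 will be asked to return" for the Visit 8 procedures. The plan does not say whether that reading can enter the Week 4 comparison.

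**The concern.** A two-sample test of Week 4 means with no missing-data rule can use only subjects who have a Week 4 value. Enrolling 6 more restores the number analysed. It does not restore the information about who was lost.

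In an equivalence trial this matters in one direction in particular. If the EVPOME subjects who leave are the ones healing poorly, those who remain look better, the observed difference shrinks toward zero, and the error favours the trial's claim. The timing makes this plausible: Section 6.2.6 says that a graft which fails will do so in the first 4 weeks, which is the window before the primary reading.

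For a subject who leaves after Visit 5, the plan already holds a Week 2 KM reading that bears on this, and it already accepts a model that could use it. As written, the primary outcome has weaker protection against dropout than pain or the Wound Healing Index.

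**Working it through.** **Inputs from the documents.** From 9.5, AIM 1: background data for POM "gave a mean measurement of 3.70 mm with an SD of 0.65 mm"; the mean difference "with 30 subjects in each arm will be approximately normal with a mean of 0 and standard error of 0.17"; margin 0.55 mm; stated power at least 80%. From 9.3: 33 randomized per arm and at most 6 lost before Week 4.

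**Assumptions not in the documents.** The arm split of the losses, who leaves, and the Week 2 to Week 4 correlation.

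**1. The plan's own figures reproduce.** SE = 0.65 × √(2/30) = 0.168 mm. Half-width = 1.96 × 0.168 = 0.329 mm, matching the 0.33 mm stated. Equivalence power at a true difference of 0 is 2Φ(0.55/0.168 − 1.96) − 1 = 81.2% (79.5% with t intervals).

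**2. Error with no bias.** At a true EVPOME deficit of 0.55 mm, false equivalence is Φ(−1.96) = 2.5%.

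**3. Bias needed to move it.** False equivalence = Φ(bias/SE − 1.96), where bias = (EVPOME leavers/33) × (KM shortfall of leavers against stayers), with POM leavers typical of their arm. A bias of 0.035 mm gives Φ(0.035/0.168 − 1.96) = 4%. That is a shortfall of 0.39 mm with 3 EVPOME leavers, or 0.19 mm with 6. A bias of 0.123 mm gives 11%: 1.35 mm with 3 leavers, or 0.68 mm with 6.

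**4. A selective-loss scenario.** Suppose 4 EVPOME subjects (those with the lowest Week 2 KM) and 2 random POM subjects leave between Weeks 2 and 4.
- Fraction lost in EVPOME: p = 4/33 = 0.121, so z = −1.17 and φ(z) = 0.201.
- Bias if Week 2 predicted Week 4 perfectly: 0.65 × 0.201/(1 − 0.121) = 0.149 mm.
- Multiply by the correlation: 0.074, 0.104 and 0.127 mm at 0.5, 0.7 and 0.85.
- SE with 29 and 31 subjects: 0.65 × √(1/29 + 1/31) = 0.168 mm.
- False equivalence: 6.5%, 9.0% and 11.4%.

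Repeated simulations with 33 per arm and t intervals agree: 6.4-6.9%, 8.7-9.5% and 11.4-12.3%. If leaving is only weighted toward low Week 2 values, they give about 4-6%.

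**5. How far the result depends on the scenario (simulated).**

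| Loss before Week 4 | Correlation | False equivalence, Week 4 test |
|---|---|---|
| Random | 0.3-0.7 | about 2.5% |
| 3 per arm, lowest Week 2 healers in both arms | 0.5-0.85 | about 2.5-3.4% |
| 1 per arm in this window, selective in EVPOME only | 0.5-0.85 | 3.5-4.5% |
| 2 EVPOME, 1 POM in this window, selective in EVPOME only | 0.5-0.85 | 4.5-6.6% |
| 4 EVPOME, 2 POM, selective in both arms | 0.5-0.85 | 4.3-6.9% |
| 4 EVPOME, 2 POM, selective in EVPOME only | 0.2-0.3 | 3.8-4.4% |

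**6. What the Week 2 reading recovers.** The likelihood estimate shifts each arm's Week 4 mean by the Week 4-on-Week 2 slope times the gap between the Week 2 mean of all subjects and that of the stayers. When Week 2 KM drives the loss, false equivalence returns to 2.4-2.8%. When the unseen Week 4 value drives it (correlations 0.3-0.7), the rate falls only from 11-12% to 7-10% with 3 leavers per arm, and from 26-27% to 12-23% with all 6 in EVPOME. Under random loss, power moves from about 79-80% to 80-84%, so nothing is given up.

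**The case against.** The strongest reply is that the inflation comes from stacked assumptions. Section 9.3 supports only a total of 6. It does not say that they leave between Weeks 2 and 4, that most come from EVPOME, or that they heal poorly. Section 8 gives HIV and cancer requiring radiation as examples of reasons for discontinuation, not poor healing. A reader might take 4-12% as the error rate this trial will have. The documents do not support that: balanced or random loss leaves the rate near 2.5%.

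Other stronger readings also fail:

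- **That the plan states a completers-only analysis.** It does not. This is inferred from a test of means with no missing-data rule, read with Section 9.3. The mixed-model paragraph gives examples rather than a closed list, but nothing ties it to AIM 1.
- **That Week 8 and Week 24 readings rescue early leavers.** A subject who left before Week 4 has no such readings. They help only someone who misses Visit 6 and continues.
- **That the model removes the bias.** It does so only if observed KM explains the loss. Section 6.2.6 describes a stent in place for the first 2 weeks and immature tissue at Week 3, so Week 2 KM may predict Week 4 only modestly.
- **That all losses are covered.** The one EVPOME-only exit the documents describe (Section 6.2.3: failed fabrication, then refusal of a second biopsy) happens before grafting. Those subjects have no post-graft KM and need separate handling.
- **That the exit visit in 6.2.11 should be moved into the Week 4 window.** That would be a protocol change, and this point does not need it.

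These objections limit the size of the claim and shape the remedy. None is a reason to prefer the Week 4 test, which needs a stronger assumption about why subjects leave.

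**Conclusion.** The point holds in conditional form. The primary analysis has no stated analysis set or missing-data rule and is in effect restricted to subjects with a Week 4 reading, although a Week 2 KM reading and a suitable model are already in the plan.

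The 4-12% figure rests on an assumed 4:2 split of the 6 losses, selection of low Week 2 healers in EVPOME only, and an assumed correlation of 0.5 to 0.85. It is a measure of vulnerability, not a forecast. Confidence that the plan is silent is high; confidence in the size is medium. The change is worth making because it is cheap and loses nothing when loss is harmless.

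**What to change.** In Section 9.5, AIM 1:

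1. Make the primary analysis a linear mixed model of KM width at Visits 5, 6, 7 and 8, with arm, visit as a category and arm-by-visit, unstructured within-subject covariance and small-sample degrees of freedom. The primary estimate is the Week 4 arm contrast, with its 95% CI judged against ±0.55 mm.
2. Analyse subjects as randomized. Report by arm those never grafted and those with no post-graft KM, and include them in the sensitivity analysis.
3. Add a sensitivity analysis that shifts missing EVPOME Week 4 values step by step toward non-equivalence, and report the shift at which the conclusion changes.
4. Keep the two-sample Week 4 test as a secondary analysis.

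**Cost.** SAP wording only, with no extra subjects, visits or measurements. With complete data the model gives the same Week 4 difference as the two-sample comparison. The small downside is its assumption that missingness depends on KM already observed; item 3 is there to test that.

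One related matter needs reconciling: the Synopsis and Section 3 randomize 60, while Section 9.3 enrols 66. The calculations above use 66. Six losses from 60 would leave 54.
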